4.1 OVERVIEW OF STUDY DESIGN

This study is designed as a Phase 2, multicenter, single-arm trial to evaluate the PFS of umbralisib in CLL patients requiring therapy who are intolerant to prior kinase inhibitor therapy. Up to 55 patients who have discontinued their prior therapy with a BTK or PI3K-delta inhibitor due to intolerance, may be enrolled.

Study Schema

All toxicity must resolve to ≤ Grade 1 prior to TGR-1202 dosing

4.2 REGISTRATION/ENROLLMENT

Following Screening, qualified patients will receive the following:

/ not progression.

Umbralisib at 800 mg once daily

Investigators will use an interactive web response system (IWRS) to enroll patients to study TGR-1202-201. Upon entering patient information into the IWRS, investigators will receive a unique patient identifier. This confirmation must be received by the site prior to dispensing study drug to the participant. Further details about the patient registration process using the IWRS system will be outlined in the Study Manual.

During the study period, all patients will be evaluated for response by CT and/or MRI during Cycles TGR-1202-201-CLL

Dated: 05 March 2019 (Ver. 5.0) Page 27 of 71

3, 6, 9, 12 and at least every 6 cycles for 24 cycles, then every 12 cycles thereafter or more frequent if warranted

(+/- 14 day window). Patients will be treated until disease progression, unacceptable toxicity, or the end of the study. Upon the end of the study, patients without disease progression may be transitioned to an open label compassionate use study.

4.3 STUDY SITES

Up to 20 centers in the United States may be asked to participate in this study. Enrollment is expected to be completed in approximately 12 months.

4.4 DISCONTINUATION FROM STUDY TREATMENT

Patients will be discontinued from study treatment for any of the following reasons:

- Disease progression
- Intolerable toxicity related to study drug
- · Patient requests to withdraw consent or discontinue treatment
- Pregnancy
- Inability of the patient to comply with study requirements
- · Conditions requiring therapeutic intervention not permitted by the protocol
- Non-compliance/lost to follow-up
- Investigator discretion
- · Discontinuation of the study by the Sponsor

Patients who discontinue from study treatment (for reasons other than progressive disease) should continue to be followed for progression as per the Study Assessment Table.

After withdrawal from protocol treatment, patients should be followed for AEs for 30 calendar days after their last dose of study drug. All new AEs occurring during this period must be reported and followed until resolution, unless, in the opinion of the investigator, these values are not likely to improve because of the underlying disease. In this case the investigators must record his or her reasoning for this decision in the patient's medical records and as a comment on the electronic Case Report Form (eCRF).

All patients who have CTCAE Grade 3 or 4 laboratory abnormalities at the time of withdrawal should be followed until the laboratory values have returned to Grade 1 or 2, unless in the opinion of the investigator, it is not likely that these values are to improve because of the underlying disease. In this case, the investigator must record his or her reasoning for making this decision in the patient's medical records and as a comment on the eCRF.

5 STUDY ASSESSMENTS AND TREATMENT SCHEDULE

Error! Reference source not found. The Table below lists study assessments that should be performed at each study visit.

STUDY ASSESSMENTS AND TREATMENT SCHEDULE

All cycles are 28 days	Screening	Cycle 1 ¹		Cycles 2 - 6 ²	> Cycle 6 ³	ЕОТ	30 day	
	D-30 to D0	D1	D8	D15	D1	Every 3 cycles	EOI	F/U
Informed Consent	X							
Medical History	X							
ECOG Performance Status	X	X			X	X	X	
Physical Examination/Vitals (Weight, Temp, BP, HR, RR)	X	X	X	X	X	x	X	
EKG (QtcF)	X							
Serology HCV, HBV, CMV	X4							
CMV surveillance					C3&6	X5		
Hematology	X	X	X	X	X	X	X	
Chemistry	X	X	X	X	X	X	X	
CT Imaging (neck, chest, abdomen, pelvis)	X ⁶	During Cycles 3, 6, 9, 12 and at least every 6 cycles for 24 cycles, then every 12 cycles thereafter or more frequent if warranted (+/- 14 days)			X ⁷			
Serum Pregnancy Test	X8		1					
Urine Pregnancy Test ⁹					X	X		
Collect Buccal Swab for Somatic DNA ¹⁰	Х							
Correlative Labs (PB) ¹⁰	Х				Cycle 2		Disease progression	
Peripheral Blood ¹¹	X							
Umbralisib	Daily Days 1 - 28							
Bone Marrow Biopsy ¹²	X							
AE Assessment		X	X	X	X	X	X	X13
Con med Assessment		X	X	X	X	X	X	

¹ Physical Exam, Vitals, ECOG, treatment administration, AEs, conmeds, hematology, serum chemistry visit days have +/- 1 day window. Assessments must be done within the specified window, but only prior to initiation of next cycle.

² Physical Exam, Vital Signs, ECOG PS, treatment administration, AEs, conmeds, hematology, serum chemistry visit days have +/- 3 day window in Cycles 2 - 6. Assessments must be done prior to treatment administration. Assessments must be done within the specified window, but only prior to initiation of next cycle.

³ Physical Exam, Vital Signs, ECOG PS, treatment administration, AEs, conmeds, hematology, serum chemistry visit days have +/- 7 day window for Cycles > 6. Assessments must be done prior to treatment administration. Assessments must be done within the specified window, but only prior to initiation of next cycle.
4 Serum virology to include HBsAg, HBsAb, HBc antibody, HCV antibody and CMV. If HBc antibody, HCV antibody or CMV is positive, subjects must be evaluated for the presence of active HBV, HCV or CMV by DNA (PCR).

⁵ Every 3 months CMV screening by PCR. CMV surveillance will discontinue 30 days after last dose of umbralisib, or as otherwise clinically indicated per investigator discretion.

⁶ Baseline CT scan within 30 days prior to Cycle 1/Day 1; then during cycles 3, 6, 9, 12 and at least every 6 cycles for 24 cycles, then every 12 cycles thereafter or more frequent if warranted (+/- 14 days). CT imaging should be performed at EOT visit if it hasn't been completed within past 30 days.

⁷ If discontinued due to reasons other than progression, follow up every 3 months on status of disease progression. Patients who discontinue from study

⁷ If discontinued due to reasons other than progression, follow up every 3 months on status of disease progression. Patients who discontinue from study treatment after cycle 12 (for reasons other than disease progression) should be followed for progression, approximately every 6 months for 24 months then every 12 months or more frequent if warranted.

⁸ Serum pregnancy test within 72 hours prior to starting treatment on Cycle 1 / Day 1.

⁹ Urine pregnancy test within 72 hours of Day 1 of each cycle. Administer test with each drug dispensation after Cycle 6.

¹⁰ Peripheral Blood (screening, Cycle 2/Day 1 and at disease progression) and buccal swab (screening only) samples for correlative analyses. See lab manual.

¹¹ Additional peripheral blood sample will be collected at screening only and analyzed at central lab for high-risk cytogenetics as well as BTK/PI3K resistance and activating mutations/deletions of prognostic value.

¹² Bone Marrow aspirate/ biopsy performed at baseline at the discretion of investigator to evaluate cytopenias. Bone marrow to be repeated if patient meets clinical criteria for CR to confirm this finding, as per iwCLL criteria.

¹³ Subjects who discontinue study drug should have a follow up visit or telephone call to assess for AEs. This should be done 30 days (+/- 7 days) after the last dose of study drug. In addition, SAEs will be reported for 30 days after the last dose of study drug.

Laboratory assessments will be collected as specified in the study assessments and treatment schema. Please refer to the study/lab manual for instructions outlining collection and shipment procedures for lab samples for central review.

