6.3 DOSING DELAYS AND MODIFICATIONS

Subjects should be assessed clinically for toxicity at each visit using the NCI CTCAE v4.0 (http://evs.nci.nih.gov/ftp1/CTCAE/CTCAE 4.03 2010-06-14 QuickReference 8.5x11.pdfError! Hyperlink reference not valid.) grading scale. Dose delay and/or modification guidance is for adverse events considered at least possibly related to the study drug. If cytopenias are deemed related to the underlying disease rather than study drug, dose modifications are not required and are per investigator discretion. Supportive care should be considered for any subject who experiences Grade \geq 2 cytopenias, or Grade \geq 1 non-hematologic toxicities. Delay of study drug is allowed for recovery of hematologic toxicities to \leq Grade 3 or non-hematologic toxicities to \leq Grade 2 or to baseline level.

If greater than 2-cycle drug delay is necessary for recovery of toxicities, you may contact TG Therapeutics prior to re-initiating study drug with any questions. If a subject discontinues study drug due to toxicity, the subject should continue to be followed for progression as described in the Study Assessments and Treatment Schedule. If a subject withdraws consent or has documented progression, an end of study visit should be completed.

Subjects should be re-educated if a dose modification occurs, to ensure they are aware of the revised number of study drug tablets. The IWRS system should be updated in the event of dose delays and/or modifications in IWRS. Contact sponsor with questions regarding dose delay and/or modification.

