10.3 ADVERSE EVENTS (AE'S) AND TREATMENT EMERGENT ADVERSE EVENTS (TEAE'S)

All AEs and SAEs occurring on study will be listed by subject. The frequency and percentages of subjects with treatment-emergent adverse events (TEAEs) will be tabulated by system organ class (SOC) and preferred term (PT), where treatment-emergent is defined as any AE that:

- Occurs after first dosing of study medication (Cycle 1/Day 1) and through the end of the study or up through 30 days (+/-7 days) after the last dose of study treatment, or
- · Is considered treatment-related regardless of the start date of the event, or
- Is present before first dosing of study medication but worsens in intensity or the investigator subsequently considers treatment-related.

TEAEs that are considered at least possibly related to study treatment will be tabulated as well as deaths, SAEs, and events resulting in treatment discontinuation.

AEs that occur after informed consent but before first dosing of study medication will not be summarized but will be listed.

At each level of summarization, a subject will be counted only once for each AE, SOC, or PT experienced within that level. In the summation for AE severity, within each level of AE, SOC, or PT experienced, the one with the highest severity will be included. In the summation for AE's relationship to the study drug, within each level of AE, SOC, or PT experienced, the one with the closest relationship to the study drug will be included.

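### The one scheduled adverse-event contact after end of treatment may fall on day 23 of a 30-day reporting period, and the sections do not agree on when that period ends

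*Combined protocol and SAP*

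**What the plan says.** **The contact.** In the Section 5 schedule, the only AE entry after the EOT visit is the 30-day follow-up. Footnote 13 allows a visit or a telephone call and times it as follows: "This should be done 30 days (+/- 7 days) after the last dose of study drug". The same footnote sets the serious adverse event (SAE) period without a tolerance: "SAEs will be reported for 30 days after the last dose of study drug". Section 10.5.2 also uses 30 days for SAEs. Later follow-up under footnote 7 concerns disease status: "If discontinued due to reasons other than progression, follow up every 3 months on status of disease progression".

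**The period.**
- Section 4.4 uses a fixed length counted from last dose: "patients should be followed for AEs for 30 calendar days after their last dose of study drug". It adds: "All new AEs occurring during this period must be reported and followed until resolution".
- Section 10.3, which defines treatment-emergent adverse events (TEAEs) for the tables, runs "through the end of the study or up through 30 days (+/-7 days) after the last dose of study treatment". It also counts any event that "Is considered treatment-related regardless of the start date of the event".
- Section 10.4.1 has AEs recorded for 30 days, give or take 7, counted from when treatment is discontinued or completed.
- Section 10.4.3 gives the same length and starting point as 10.4.1. Its last sentence then limits reporting after 30 days to events judged treatment-related.

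**The concern.** There are two separate matters.

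The first is ascertainment. A reporting period works best when someone asks about events at or after its end. Footnote 13 permits the asking to stop a week before the 4.4 period closes and requires no second call. Non-serious events that the subject does not volunteer in that week may be missed, and SAEs in that week also go unprompted.

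The second is definition. A tolerance of 7 days either way suits a visit date. Attached to the end of a reporting or treatment-emergence period, it leaves no single cut-off. Sites may stop recording unrelated events on different days, and a programmer must choose a day and a limb of 10.3 before the TEAE flag can be derived.

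At stake are the completeness and consistency of late AE counts. Safety relative to the prior kinase inhibitor is a key secondary objective (Section 2.1), and TEAE frequencies are the planned tabulation. The efficacy analyses do not use this period.

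**Working it through.** The plan states no figure on this point to reproduce. The check is day counting and a side-by-side reading.

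**Contact timing, with 4.4 read as fixed**
- Inputs: contact at day 30 with 7 days either way (footnote 13); AE period of 30 days from last dose (4.4).
- Earliest contact: 30 − 7 = day 23. Latest: 30 + 7 = day 37.
- Days after the earliest contact but inside the period: 24 to 30, which is 30 − 23 = 7 days. Share: 7/30 = 23.3%.
- A contact on day 30 or later leaves 0 days.

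**Contact timing, with the period read as closing at the contact (10.3, 10.4.1, 10.4.3)**
- There is no unprompted gap for non-serious AEs. SAEs still run to day 30 under footnote 13 and 10.5.2.
- The period can end from day 23 to day 37, a spread of 37 − 23 = 14 days.

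The 7-day gap and the 14-day spread belong to different readings and should not be added.

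**Statements of the AE period**

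| Place | Length | Counted from |
|---|---|---|
| 4.4 | 30 days, fixed | last dose |
| 10.3 | 30 days ± 7, or study end | last dose |
| 10.4.1 | 30 days ± 7 | discontinuation or completion |
| 10.4.3, earlier sentence | 30 days ± 7 | discontinuation or completion |
| 10.4.3, last sentence | 30 days, no tolerance | not stated |

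**Worked case.** Take an unrelated AE on day 34, with no dose hold, so that the two starting points coincide. It lies outside the 4.4 period. It can be treatment-emergent under 10.3 and recordable under 10.4.1, because 34 is below 37. The last sentence of 10.4.3, read literally, says not to report it.

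**After the proposed fix.** With the contact at day 30 to 37 and the period ending on day 30, the largest unprompted gap falls from 7 days to 0.

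**The case against.** The strongest reply is that three statements carry the same tolerance as footnote 13 and so describe a period that closes at the contact. On that reading the 7-day gap disappears for non-serious AEs. This is a fair reading of Section 10, but 4.4 still fixes 30 days and demands every new AE within them. The last sentence of 10.4.3 may also be shorthand for the period defined earlier in its paragraph. That would remove the conflict inside 10.4.3, but not the one with 4.4 or the movable end date.

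Other protections also stand. AEs that lead to discontinuation are followed to resolution or stabilization (10.4.3), Grade 3 or 4 laboratory abnormalities at withdrawal are followed (4.4), and related events remain reportable later.

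Three stronger readings are tempting, and the documents do not support them.
- *All four sections differ from one another.* They do not. Sections 10.4.1 and 10.4.3 share a length and a starting point, and 4.4 and 10.3 both count from last dose.
- *The two starting points can lie more than 56 days apart.* Section 6.3 does contemplate long holds ("If greater than 2-cycle drug delay is necessary for recovery of toxicities"), and 2 cycles × 28 days = 56 days. That sentence, however, is about contacting the sponsor before restarting drug. The figure also assumes that discontinuation is dated at a later decision to stop, a date that the documents do not define. Without a hold the difference is about zero.
- *The study-end limb of 10.3 is simply open-ended.* It has a plausible purpose. Subjects without progression may move to a compassionate use study (4.2, 9.7) and may have no last dose within this one.

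**Conclusion.** The point holds as a minor one. Footnote 13 permits a contact that leaves up to 7 of the 30 days in 4.4 without a scheduled AE prompt. Separately, the AE and TEAE period has no single determinate end: on the tolerance readings it can fall anywhere from day 23 to day 37.

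The 23% is a worst case. It rests on the fixed reading of 4.4 and on a contact at the earliest limit. A reader might infer that 23% of post-treatment events are lost. The documents do not show this, because the reporting duty continues to day 30 and no AE rate is given for these days, so the number of events affected cannot be estimated.

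The consequence is confined to descriptive safety counts in a single-arm study, mainly for unrelated events. PFS, the other efficacy analyses and the sample size are untouched.

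**What to change.** 1. **Footnote 13.** Set the contact at 30 days after last dose with a window of +7 days only, or require a repeat call on or after day 30 if the first is made earlier.
2. **One period in 4.4, 10.3, 10.4.1 and 10.4.3.** Use Cycle 1/Day 1 through 30 days after last dose. Remove the 7-day tolerance from the period definitions and keep +7 days only as the contact window. State two special cases:
   - Subjects still on drug who transfer to compassionate use: end the period when their participation in this study ends.
   - Subjects who stop after a hold longer than 30 days: run the period to the EOT visit, so that events during the hold are not cut off.
3. **Related events.** Keep treatment-related events reportable and counted at any time.

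The cost is an amendment to wording, which goes through site IRB review under 11.2, slightly less scheduling flexibility, and one extra call where the first was early. Unrelated events on days 31 to 37 leave the TEAE tables, though any that are entered can still be listed.

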5.1.1 LOCAL LABORATORY ASSESSMENTS

Hematologic profile and serum chemistry to include (within 30 days of Cycle 1/Day 1):

Hematologic Profile						
Hematocrit	Neutrophils	Platelet count				
Hemoglobin	Lymphocytes	Absolute lymphocyte count				
Erythrocyte count	Monocytes	Leukocyte count				
Basophils	Eosinophils	Absolute neutrophil count				
Serum Chemistry						
Albumin	Creatinine	SGOT [AST]				
Alkaline phosphatase	Glucose	SGPT [ALT]				
Bicarbonate/CO2	LDH	Sodium				
BUN	Magnesium	Total bilirubin				
Calcium	Phosphorus	Total protein				
Chloride	Potassium	Uric acid				

Hematologic and Serum Chemistry windows as follows:

- Cycle 1: 1 day window
- Cycles 2 6: 3 day window
- > Cycle 6: 7 day window
- Serum β-HCG test.
- Serum Virology to include HBsAG, HbSAb, HBc antibody, HCV antibody, and CMV. If HBc antibody, HCV antibody or CMV are positive the subject must be evaluated for the presence of active HBV, HCV or CMV by DNA (PCR) - See Appendix D.
- 4. Baseline bone marrow aspirate/biopsy (if indicated or warranted).
- CMV surveillance every 3 months by PCR. CMV surveillance will discontinue 30 days after last dose of umbralisib, or as otherwise clinically indicated per investigator discretion.

5.1.2 CENTRAL LABORATORY ASSESSMENTS

See Study Lab Manual for full Central Lab details (collection, preparation, shipping, etc.)

- Peripheral Blood sample at screening, Cycle 2/Day 1 and at disease progression, will be collected, shipped and stored at for correlative analyses. See Study/Lab Manual for details.
- An additional peripheral blood sample will be collected at screening only and analyzed by at central lab for cytogenetics (17p del, 11q del, p53 mutation) and BTK/PI3K resistance and activating mutations/deletions of prognostic value. In addition, a Buccal Swab will be collected at screening only and sent to central lab for analysis (See Study/Lab Manual).

6.1 TREATMENT SUMMARY

Treatment will be administered on an outpatient basis in 4-week (28 day) cycles.

Umbralisib

- 800 mg umbralisib once daily until removal from study
- · Patient diary will be utilized to document missed doses of study drug

6.2 AGENT ADMINISTRATION

Umbralisib will be self-administered orally, all on an outpatient basis.

6.2.1 GUIDELINES FOR ADMINISTRATION OF UMBRALISIB

- Method of Administration: Umbralisib will be administered orally once daily with food
- Potential Drug Interactions: No drug interactions have been reported to date.
- Anti-microbial prophylaxis: Subjects are required to start prophylaxis treatment with pneumocystis jiroveci pneumonia (PJP) and antiviral therapy prior to Cycle 1 Day 1. Choice of PJP and anti-viral prophylaxis therapy is per investigator discretion and institutional standard of care, with the following as recommendations:
 - o Anti-viral Prophylaxis: Valtrex 500 mg daily or Acyclovir 400 mg BID or equivalent.
 - PIP Prophylaxis: Dapsone 100 mg daily or equivalent.

If anti-viral or anti-bacterial prophylaxis is not tolerated, alternating to a different prophylactic agent, reducing the dose or modifying the schedule for the prophylactic agent, or discontinuing prophylaxis is at the discretion of the investigator. Final choice of PJP and anti-viral prophylaxis therapy is per investigator discretion.

Pre-medications: None

Umbralisib will be dispensed at the sites by the Pharmacist of authorized designee. Subjects must be provided drug in its original container. Subjects should be instructed to return any unused tablets when they return the bottle to the site. Study drug compliance should be reviewed with the subject at the beginning of each new treatment cycle and as needed. Missed doses will be documented in the subjects' medical record.

Umbralisib will be self-administered (by the subject). Tablets should be taken approximately the same time each day with food (within 30 minutes of a meal). Subjects should be instructed to swallow the tablets whole. Do not chew or crush umbralisib.

If a dose of umbralisib is missed, it should be taken as soon as possible on the same day. If it is missed for greater than 12 hours, it should not be replaced. If vomiting occurs, no attempt should be made to replace the vomited dose.

TGR-1202-201-CLL

6.2.1.1 DISPENSING OF UMBRALISIB

Before dispensing, the Pharmacist or authorized designee must check that the umbralisib is in accordance with the product specifications and the validity is within the re-test date.

The exact dose and the date of administration of umbralisib must be recorded within the eCRF, subject's medical records. For the purpose of drug accountability and dosing, a drug diary will be utilized. Any error in drug administration should be recorded (e.g., missed dose) in the eCRF.

The Pharmacist or authorized designee should record the date dispensed and subject's number and initials, as well as complete the accountability record in the electronic drug accountability system with information concerning the dispensation of umbralisib.

